### B2. SIGNIFICANCE AND BACKGROUND FOR THE STUDY

Advanced chronic liver disease/cirrhosis creates a state of relative immune-compromise, and, indeed, infections are a key precipitant of clinical decline in patients with cirrhosis. Specifically, infections of any kind are a common cause of acute on chronic liver failure (ACLF) and complicate 20-40% of hospital admissions of patients with cirrhosis. Although other pathogens are also important, the vast majority of infections in patients with cirrhosis are of bacterial origin. In other high-risk hospitalized patient populations, early initiation of antibiotics has been shown to reduce the need for intensive care unit (ICU) admission and short-term mortality. Unfortunately, the presentation of infection in patients with cirrhosis is protean and may be subtle. Diagnosis may be delayed by the absence of classic signs of infection such as fever and absolute leukocytosis. Vital diagnostic studies, such as paracentesis or other culture (blood, urine, or sputum) may be delayed or may not yield results until days after presentation. Delaying antibiotics until such studies result is inadvisable in patients with infection; however, empiric administration of antibiotics to all patients with cirrhosis admitted to the hospital would result in waste and increased risk of antibiotic resistance, *Clostridium difficile* infection, and other adverse effects. Sub-groups of patients with cirrhosis are already known to benefit from empiric/prophylactic antibiotics including those with acute upper gastrointestinal hemorrhage and those with increased risk of spontaneous bacterial peritonitis. The risk of infection increases with more advanced cirrhosis, as marked by higher Model for End-stage Liver Disease – Sodium (MELD-Na).

There are also biomarkers of systemic infection that, although not specific, may be used to identify patients more likely to have an active infection and thus allow more targeted use of empiric antibiotics. Specifically, increase in serum C-reactive protein (CRP, >25 mg/L) and Procalcitonin (>0.5 ng/mL) are associated with acute bacterial infection.

These factors may permit identification of patients who would benefit from prophylactic/empiric antibiotics. There has not, however, been investigation of the effect of prophylactic antibiotics on hospitalized patients with advanced cirrhosis beyond the sub-populations described above.

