## B. Statistical Considerations

**Sample Size Justification:** We estimate there will be a small prevalence of occult infection among patients who are believed to be eligible after initial screening is completed. Patients with identified infection at the time of enrollment will not be randomized and instead be treated as per standard of care at the discretion of the medical staff. We estimate there may be 5-10 such patients who are thus enrolled but not randomized.

We aim to randomize a total of 40 subjects, assigned to active intervention vs. placebo; hence as many as 50 may be screened / consented to determine eligibility. This is a pilot study intended to assess feasibility of patient identification, administration of required testing and enrollment processing, and the rate thereof. The magnitude of observed effect will permit sample size estimation for a larger, more definitive study which we hope to complete subsequently. It is unknown how many subjects will need to be screened to complete this planned enrollment. We will also obtain information on the dropout rate and/or rate of use of therapeutic antibiotics which may alter enrollment goals for a future study.

**Data Analysis:** As stated elsewhere, the proposed study is a pilot study, not intended to provide definitive results. However, there are multiple outcomes of interest that will be recorded in order to permit planning of a future study.

The primary outcome is incident bacterial infection identified after randomization

screening (as defined below).

Secondary outcomes include:

1. In-hospital mortality;
2. 30-day mortality;
3. Incident acute on chronic liver failure (ACLF) defined as two or more of:
  - Grade 3-4 hepatic encephalopathy,
  - Need for renal replacement therapy,
  - Need for mechanical ventilation,
  - Need for vasopressors, or mean arterial pressure (MAP) <60 mmHg, or decrement of >40 mmHg in systolic blood pressure after volume resuscitation.
4. Change in calculated CLIF-C ACLF score;
5. Length of stay (LOS) after randomization;
6. Intensive Care Unit (ICU) transfer after randomization;
7. C difficile infection (positive stool polymerase chain reaction (PCR) or toxin-assay in the setting of diarrhea);
8. Increment in MELD-Na  $\geq 3$  points between randomization and discharge;
9. Acute kidney injury (increase in creatinine  $\geq 0.3$  mg/dL in 48 hr or  $>50\%$  from baseline (within previous 3 months) occurring after randomization;
10. Variceal hemorrhage.

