Covariates recorded/measured

- Procalcitonin at enrollment
- C-reactive protein at enrollment
- Other antibiotic use in-hospital (type and duration)
- Fungal infections (by positive culture) or use of systemic anti-fungal medications.

We will monitor daily for the incidence of the outcomes above via review of the medical record and discussions with the inpatient providers (when necessary). For any subject with a positive culture result, the site, organism, and antibiotic susceptibility will be recorded when available.

Infection definitions

- Bacteremia (positive blood culture not felt to be a skin flora contaminant)
- Spontaneous bacterial peritonitis (ascites PMN count  $>250/\mu\text{L}$  or positive ascites culture in the setting of new abdominal pain, or unexplained leukocytosis, fever, hypotension, fever, acute kidney injury, or exacerbation of hepatic encephalopathy, i.e., increase in West Have grade)
- Pneumonia: Pulmonary infiltrate on chest x-ray (CXR) or computed tomography (CT) in the presence of A) respiratory symptom(s) (cough, pleuritic pain, or dyspnea) or B) auscultation findings, abnormal body temperature ( $>38\text{C}$  or  $<36\text{C}$ ), or newly abnormal leukocyte count  $>10,000/\text{microL}$  or  $<4,000/\text{microL}$  (if baseline leukocyte count  $>4,500/\text{microL}$ ).
- Skin or Soft Tissue Infection (SSTI): Superficial erythema, warmth, or fluctuance in the

skin/soft tissues felt to be secondary to infection by the inpatient team, excluding mild superficial thrombophlebitis from IV catheter insertion

- UTI: Urine leukocytes  $> 10/\text{hpf}$ , bacteruria, positive urine culture, urinary leukocyte esterase or nitrite in the presence of symptoms/signs of infection (dysuria, unexplained increased urinary frequency, fever, or leukocytosis)
- Other infections as identified by the primary medical team

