For purposes of analysis, deidentified subject clinical data documenting the metrics above will be stored in a password protected file within the BIDMC network. Analysis will be conducted at BIDMC using R-studio software. There are no additional statistical consultants currently affiliated with this study. Descriptive statistics will include the incidence of the primary and secondary categorical outcomes in each arm with comparison via Chi-square test or Fisher's exact test for rare events. As noted elsewhere, we do not anticipate this study will provide sufficient statistical power to demonstrate statistically significant differences between groups, but we will need to have an idea of the magnitude of effect prior to planning such a study and hope to obtain this information here.

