#### B5. POSSIBLE RISKS AND ANALYSIS OF RISK/BENEFIT RATIO

Risks of participation in the study include reaction to the antibiotic used in the trial: Ceftriaxone is commonly used to treat patients with end stage liver disease, and subjects may be prescribed ceftriaxone as routine care even if they do not participate in this trial.

Regardless of which treatment the subject is assigned, the study medication will be administered intravenously (IV), peripherally or via central venous catheter if one is already in place for routine care.

Side effects rarely observed in patients receiving any type of fluid intravenously include fever, infection at the site of IV insertion, blood clot in the vein, or inflammation of the vein extending from the site of injection, IV fluid leakage into the tissue around the IV insertion, and fluid overload.

Subjects randomized to receive **ceftriaxone**, may experience side effects that have been observed in prior clinical trials.

- The most common side effects (>10%) observed in clinical trials of ceftriaxone include skin tightness, thickening of the skin, and a warm sensation around the site of the injection when ceftriaxone was administered as an intermuscular injection.
- Less common side effects (<10%) included pain and tenderness at the injection site when the drug is given as an intermuscular injection; skin rash, diarrhea, eosinophilia (excess of inflammatory/allergic blood cells), thrombocytopenia (excess of platelets/blood clotting-cells), leukopenia (low level of white/infection-fighting blood cells), increased serum transaminases (liver blood tests which may suggest liver injury) and increased blood urea nitrogen (a marker of kidney function).
- Allergic reaction to the study drug which can vary in severity from asymptomatic rash, to pruritic (itchy) rash, to hives, to anaphylaxis (a life threatening allergic reaction).
- Indirect adverse effect of the study drug: development of antibiotic resistance,

opportunistic infection- *C difficile* colitis or fungal infection. Diagnostic uncertainty related to treatment of subsequent infections.

Subjects randomized to receive **placebo**, will receive approximately 100 mL (less than 7 tablespoons) of normal saline. There are no additional side effects expected beyond those listed above.

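### Two of the three indirect harms the protocol attributes to ceftriaxone, fungal infection and antibiotic resistance, are not outcomes and have no planned by-arm comparison; nor do adverse events as a class

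*Combined protocol and SAP*

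**What the plan says.** Section B5, on risks, lists as a consequence of treatment: "Indirect adverse effect of the study drug: development of antibiotic resistance", followed by opportunistic infection in the form of C. difficile "colitis or fungal infection. Diagnostic uncertainty related to treatment of subsequent infections". Section B2 uses part of the same list as the argument against treating every admitted patient with cirrhosis, which it says "would result in waste and increased risk of antibiotic resistance", C. difficile infection and other adverse effects.

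The Statistical Considerations (section B3, part B) handle the three harms differently:

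- **C. difficile** is secondary outcome 7, with a definition: "C difficile infection (positive stool polymerase chain reaction (PCR) or toxin-assay in the setting of diarrhea").
- **Fungal infection** appears under the heading "Covariates recorded/measured", as "Fungal infections (by positive culture) or use of systemic anti-fungal medications". It shares that list with procalcitonin and C-reactive protein at enrollment and with other in-hospital antibiotic use.
- **Resistance** appears only as a recording instruction: "For any subject with a positive culture result, the site, organism, and antibiotic susceptibility will be recorded when available".

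The analysis paragraph then states: "Descriptive statistics will include the incidence of the primary and secondary categorical outcomes in each arm", compared by chi-square or Fisher's exact test. Adverse events are coded, graded and classified under section B3, part A, and the principal investigator reviews the non-serious ones after the first 5 randomized subjects and after every 10 thereafter. The same part states that investigators are blinded.

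**The concern.** A covariate is normally a characteristic fixed before treatment. Procalcitonin and C-reactive protein at enrollment fit that description. Fungal infection and antifungal use carry no enrollment time point, can begin after randomization, and are named by the protocol itself as possible effects of study drug. They behave as outcomes but are filed where the by-arm analysis does not reach them. Resistance has neither a definition nor an outcome.

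The pilot exists to plan a larger trial of antibiotics in all patients with advanced cirrhosis admitted without an indication for them, and the analysis section says it hopes to learn the size of effects. Followed as written, it would compare infection, the other clinical outcomes and C. difficile between arms. An excess of fungal infection on ceftriaxone would appear in no planned comparison. An excess of non-susceptible organisms would not be separated from other bacterial infections. Both bear on whether the larger trial is worth doing and on what its safety outcomes should be.

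**Working it through.** The point is mainly one of classification, so the first step sets the sections side by side.

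| Item | Named as harm (B5) | Status in B3, part B | In the planned by-arm comparison? |
|---|---|---|---|
| C. difficile | yes | secondary outcome 7 | yes |
| Fungal infection or antifungal use | yes (fungal infection) | covariate | no |
| Antibiotic resistance | yes | susceptibility recorded when available | no; a resistant bacterial infection counts in the primary outcome, without breakdown |
| Adverse events as a class | direct side effects listed | not mentioned; graded under B3, part A | no |

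Two possible rescues were checked. The infection definitions end with an open category for other infections identified by the medical team, but the primary outcome is restricted to bacterial infection, so this does not bring fungal infection in. The periodic review of non-serious adverse events is done by a blinded investigator, so as described it is not a comparison by arm.

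**The plan's own figure.** The sample size text gives 40 randomized plus 5 to 10 enrolled but not randomized: 40 + 5 = 45 and 40 + 10 = 50, which matches the stated maximum of 50. No significance level, power or event rate is given, so there is no power figure to reproduce.

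**What by-arm reporting could show.** The allocation ratio is not stated. I assume 20 per arm and show 13 and 27 as a range.

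- Upper exact 95% limit when no events are seen, two-sided: 1 − 0.025^(1/n). For n = 20 this is 16.8%; for n = 13, 24.7%; for n = 27, 12.8%. The one-sided limit for n = 20 is 1 − 0.05^(1/20) = 13.9%.
- Chance of at least one event in 20 subjects: 1 − (1 − p)^20. The documents give no fungal or resistance rate. For assumed true rates of 2%, 5% and 10% the chances are 33%, 64% and 88%.
- Fisher's exact test, two-sided: 4/20 against 0/20 gives p = 0.106; 5/20 against 0/20 gives p = 0.047. Five events against none is the smallest such split below 0.05.

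These figures support counts with intervals, not tests.

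**The case against.** The strongest reply is that this is a 40-subject feasibility pilot that disclaims definitive results and adequate power. The data will exist, so anyone can tabulate them later. The analysis text says what the statistics will include, which excludes nothing, and it stores all the recorded metrics for analysis. That much is right. A reader might infer that these harms will never be compared; the text supports only that no comparison is planned. What remains is that the choice to report them would be made after the data are seen.

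Other stronger readings also go beyond the text:

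- *That all adverse events escape comparison.* Death, ICU transfer, acute kidney injury, acute on chronic liver failure and variceal hemorrhage are categorical secondary outcomes compared by arm.
- *That resistant infections would go unseen.* A resistant bacterial infection after randomization counts in the primary outcome. Only the breakdown by susceptibility is missing.
- *That the covariate label will bias the treatment effect.* Adjusting for a post-randomization event could do so, but no adjusted model is planned.
- *That other in-hospital antibiotic use is a neglected harm.* Section B5 does not name it as one, and the sample size text gives the rate of therapeutic antibiotic use a purpose, namely planning enrollment for the next study.
- *That nearly all secondary outcomes measure only hoped-for benefit.* Section B4 names only some of them as possible benefits. Kidney injury can also show harm, since B5 lists raised blood urea nitrogen as a side effect.

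The reply is also right that a resistance outcome needs care. Cultures during treatment are left to the care team, and susceptibility is available only for some isolates.

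**Conclusion.** The concern holds in limited form. Of three indirect harms the protocol itself attributes to ceftriaxone, one is a compared outcome, one is misfiled as a covariate, and one is recorded without a definition or an outcome. No by-arm summary of adverse events as a class is planned. This is more than silence, because the plan explicitly places a possible effect of treatment among the covariates.

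Its weight is moderate. It threatens neither the feasibility aims nor the primary outcome, and the harm estimates would be coarse: with an assumed 20 per arm, even zero events leaves true rates up to 16.8% compatible with the data. The C. difficile comparison already planned has the same limit. The classification itself rests on the text alone; only the precision figures depend on the assumed split and event rates.

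**What to change.** In the Statistical Considerations:

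1. Move fungal infection or systemic antifungal use from the covariates to the secondary outcomes, as a safety outcome, restricted to events after randomization.
2. Add a safety outcome: at least one post-randomization clinical isolate reported not susceptible to ceftriaxone. Count it over all randomized subjects, because treatment may change who has a positive culture. Show by arm how many subjects were cultured and how many isolates were untested, so that a subject without a reported isolate is not read as proven free of resistance.
3. Report both outcomes, and adverse events by grade, descriptively by arm as counts with exact confidence intervals.
4. Report the already planned rate of therapeutic antibiotic use by arm, as a process measure and not as a harm.

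The sample size, treatment and data collection do not change. The cost is the wording, the rule for uncultured subjects and untested isolates, and a few more descriptive rows. Precision stays low, and the susceptibility data remain limited to cultures taken in routine care.

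### Does a C. difficile case count toward the primary outcome through the residual item for other infections, and does the plan need to say so?

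*Combined protocol and SAP*

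**What the plan says.** Section B3, part B (Statistical Considerations) states: "The primary outcome is incident bacterial infection identified after randomization", and refers to definitions given later in the same part. Those definitions cover bacteremia, spontaneous bacterial peritonitis, pneumonia, skin or soft tissue infection and urinary tract infection, and close with "Other infections as identified by the primary medical team". That last item names no organism or site and carries no exclusion. The skin and soft tissue item does carry one: "excluding mild superficial thrombophlebitis from IV catheter insertion".

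C. difficile appears separately as secondary outcome 7, with its own criterion: "C difficile infection (positive stool polymerase chain reaction (PCR) or toxin-assay in the setting of diarrhea". Section B5 lists it for the ceftriaxone arm under the label "Indirect adverse effect of the study drug", together with resistance and fungal infection.

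On analysis, the same part B says: "Descriptive statistics will include the incidence of the primary and secondary categorical outcomes in each arm", compared by Chi-square or Fisher's exact test. On the pilot's purpose it says: "The magnitude of observed effect will permit sample size estimation for a larger, more definitive study". It also says that the study is not meant to be definitive and is not expected to have power for differences between the arms.

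**The concern.** Read literally, a C. difficile infection diagnosed by the treating team is a bacterial infection that arose after randomization and was identified by that team, so it is a primary event. Its separate listing with a laboratory criterion points the other way. Two careful analysts could classify the same patient differently.

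C. difficile is not an arbitrary unlisted infection, because the protocol itself attributes it to the study drug. If it is counted, an event the drug may cause offsets events the drug is meant to prevent, and the apparent benefit would tend to shrink. Since the observed effect is to inform the size of the next trial, the definition could carry through to that calculation. Leaving it open also allows the choice to be made after the data are seen.

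**Working it through.** **The text.** Section B2 names C. difficile as a risk of empiric antibiotics, outcome 7 gives it a criterion, the exclusion criteria bar patients with recurrent episodes, and section B5 lists it as a harm. None of these places says whether a case is also a primary event. The silence is confirmed.

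**The plan's own figure.** The pilot randomizes 40, with up to 10 more consented but not randomized: 40 + 10 = 50, which agrees with the stated maximum. The 40 comes with no event rate, effect size, alpha or power, so nothing in it depends on how C. difficile is classified.

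**Assumed inputs.** The documents give no C. difficile rate, no expected effect and no allocation ratio. For illustration take:
- target infection 20% on placebo (p1) and 10% on ceftriaxone (p2);
- C. difficile rates c1 (placebo) and c2 (ceftriaxone) between 1% and 5%, independent of the other infections;
- 1:1 allocation, so 20 per arm in the pilot;
- two-sided alpha 0.05 and 80% power for the next trial.

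**Formulas.** Rate with C. difficile counted = p + (1 - p)c. Per-arm size = (1.960 + 0.842)² × [p1(1 - p1) + p2(1 - p2)] / (p1 - p2)², rounded up, using the rates for the version in question.

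**Without C. difficile.** 7.85 × (0.16 + 0.09) / 0.10² gives 197 per arm.

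**With C. difficile counted:**

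| C. difficile, placebo v ceftriaxone | Rates | Difference | Shift (points) | n per arm |
|---|---|---|---|---|
| 2% v 2% | 0.216 v 0.118 | 0.098 | -0.2 | 224 |
| 1% v 2% | 0.208 v 0.118 | 0.090 | -1.0 | 261 |
| 2% v 5% | 0.216 v 0.145 | 0.071 | -2.9 | 457 |
| 2% v 1% | 0.216 v 0.109 | 0.107 | +0.7 | 183 |
| 5% v 2% | 0.240 v 0.118 | 0.122 | +2.2 | 152 |

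If every C. difficile case also has another primary event, the rates do not change and the figure stays at 197.

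**Direction.** The change in the difference is (1 - p1)c1 - (1 - p2)c2. It is negative only when c2/c1 exceeds (1 - p1)/(1 - p2) = 0.8/0.9 = 0.89. Placebo patients may also receive antibiotics for clinical reasons, so the sign is not guaranteed.

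**Against the pilot's precision.** The standard error of the risk difference at 20 per arm is √[(0.16 + 0.09)/20] = 0.112, or 11.2 points. The largest shift in the table is 2.9/11.2, about a quarter of that. The approximate 95% interval around a true 10-point difference is 10 ± 1.96 × 11.2, or -12 to +32 points.

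**Whether the question arises at all.** The chance of no C. difficile case among 40 patients is 0.99²⁰ × 0.98²⁰ = 55% at 1% v 2%, 0.98⁴⁰ = 45% at 2% v 2%, and 0.98²⁰ × 0.95²⁰ = 24% at 2% v 5%.

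**The case for a change.** The best case for a change is that a primary outcome should have one definition, fixed before the data are seen, and that stating it costs one line. Being able to compute both versions afterwards does not answer this, because that is exactly what makes a later choice possible. In a small pilot each case is also conspicuous: with 20 per arm, one case not already counted moves an arm by 5 points. If C. difficile added 5 points in the ceftriaxone arm only, 20% v 10% would become 20% v 15%, and a pooled-variance calculation for the next trial would go from 199 to 906 per arm.

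Part of this stands. The wording is open, and a sentence settling it would do no harm. The 906 carries little weight, because it rests on a one-sided rate that the documents do not support, and even that 5-point shift is under half of the 11.2-point standard error. Nor would the test result change: 3/20 v 6/20 gives Fisher p = 0.45, and one added ceftriaxone case (4/20 v 6/20) gives p = 0.72, neither near significance.

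The contrast with the skin and soft tissue exclusion is also weak. Thrombophlebitis can look like the erythema and warmth in that definition and has no outcome line of its own, so it needs a carve-out there. C. difficile already has its own line.

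**Conclusion.** No change to the plan follows. The residual item leaves a detail unstated, but following the plan as written gives no wrong result. Including C. difficile measures the net burden of bacterial infection; excluding it measures the infections that prophylaxis targets. Reasonable statisticians differ on which to prefer. The separate outcome with its own laboratory criterion makes exclusion the more natural reading, though this is an inference and not stated text.

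The harm cannot be hidden, because outcome 7 is reported and compared by arm whichever reading is used. Whoever sizes the next trial will have both counts and can state which one was used.

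The size is unknown from the documents. On the assumed rates of 20% v 10% for target infection and 1% to 5% for C. difficile, the shift runs from -2.9 to +2.2 points and the next trial's per-arm size from 152 to 457 around 197. Those figures move in both directions and lie well inside the pilot's sampling error, so they are not evidence of damage. The conclusion rests on the pilot's stated non-definitive purpose and on infections being recorded by type for each patient, so that either version can be rebuilt.
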